# 6.3.2. Sample Size Considerations: Part B

**Part B** of the study targets healthy adults and adolescents ages 15 to 35 years who reside in ZIKV endemic or potential endemic regions. This age range is considered to be the range of the highest reproductive potential and therefore, this age group will likely be the initial target for a successful ZIKV vaccine. Additionally, the risk of GBS has been shown to increase with age, so

this study population excludes those who might be at higher perceived risk for GBS [54-56]. Randomization at each study site will equally allocate subjects to vaccine or placebo schedules. The randomization plan does not include provisions for replacing subjects with incomplete product administration or visit schedules.

A total of 2400 subjects will be randomized 1:1 to receive either the study vaccine or placebo. The study sample size was determined primarily based on the evaluation of vaccine efficacy (VE). The study also has ample sample size for detecting AEs, therefore meeting the primary endpoints.

To detect a VE of 61%, the trial aims to achieve 90 cases of naturally acquired virologic ZIKV infection within 2 to 3 years. If it appears this target is unlikely to be met, the study may be expanded to achieve this target. Prior to the completion of randomization, the combined vaccine and placebo incidence rate of subclinical ZIKV cases will be calculated. At each site, the blinded site-specific baseline seropositivity rate may be calculated and used to adjust the needed sample size and to aid in allocation of enrollment slots. Both types of rates will be used to help decide if the enrollment should be extended to allow for the target to be achieved. For planning purposes, we will allow for a total sample size of up to 15,000. Such a sample size could achieve our target number of virologic ZIKV cases within 3 years, assuming full accrual within 12 months, even if the placebo incidence rate is as low as 0.50% and the seropositive rate is as high as 30% among enrollees.

Sample size will be re-evaluated prior to the end of the randomization period to estimate if we will achieve 90 cases of virologic ZIKV infection in 2 to 3 years. This calculation will explicitly take into account the accrual rate, the dropout rate, the baseline seropositive rate, and the incidence rate. Values for these rates will be based on within trial data augmented by other information (e.g., historical dropout rates in other studies, epidemiologic projections of incidence from other sources). If this calculation suggests the sample size of 2400 is inadequate to achieve 90 cases of virologic ZIKV infection in 2 to 3 years, the sample size may be increased.

Accrual may occur rapidly at more than one site. The data managers will carefully monitor study accrual and notify the sites and Protocol Chairs when completion of accrual is near.

# 6.3.2.1. Power Calculations for Evaluation of Safety

The goal of the safety evaluation for this study is to identify safety concerns associated with administration of the investigational vaccine. Two sample size calculations for safety are expressed in terms of two approaches, within group and comparing two groups.

The ability of the study to identify safety events may be expressed in terms of the probability of observing one or more event of interest (e.g., AEs) within each group assuming a range of underlying true event rates. With 1200 subjects per group and the true event rate of 0.3%, there is a probability of 97.3% to observe at least one event and a probability of 87.5% to observe more than one event (Table 6).

Safety event rates may vary considerably with the type of event considered. Safety will be evaluated within each arm and additionally stratified by baseline ZIKV status, pre-exposed or not.

•	•••	
True Event Rate (%)	Pr (0 event) (%)	Pr (more than one event) (%)
0.01	88.7	0.7
0.05	54.9	12.2
0.10	30.1	33.7
0.30	2.7	87.5
0.50	0.2	98.3

# Table 6: Probability of Observing Safety Events within a Group (n=1200)

Table 7 provides the minimum detectable difference by two-sided chi-square test between the vaccine and placebo groups over a range of possible event rates and sample sizes as follows: 1200 samples per group, 960 samples per group to account for 20% early drop out, 480 and 240 samples per group for comparisons within a stratum defined by baseline ZIKV status.

Table 7:Minimum Detectable Difference in Event Rate Assuming Type I Two-Tail
Error Rate of 5%

Sample size	Event rate	Detectable wit	th 80% power	Detectable wi	th 90% power
group (#) (in placebo) (%)		Difference (%)	Event rate (in vaccine) (%)	Difference (%)	Event rate (in vaccine) (%)
	0.1	0.81	0.91	1.04	1.14
	0.5	1.19	1.69	1.46	1.96
1200	1.0	1.50	2.50	1.80	2.80
1200	5.0	2.80	7.80	3.29	8.29
	10.0	3.69	13.69	4.32	14.32
	25.0	5.11	30.11	5.93	30.93
	0.1	0.98	1.08	1.26	1.36
	0.5	1.39	1.89	1.71	2.21
960	1.0	1.73	2.73	2.09	3.09
	5.0	3.17	8.17	3.74	8.74
	10.0	4.16	14.16	4.88	14.88
	25.0	5.73	30.73	6.66	31.66
400	0.1	1.79	1.89	2.33	2.43
	0.5	2.30	2.80	2.88	3.38
	1.0	2.75	3.75	3.38	4.38
480	5.0	4.72	9.72	5.60	10.60
	10.0	6.08	16.08	7.15	17.15
	25.0	8.20	33.20	9.55	34.55
	0.1	3.38	3.48	4.43	4.53
	0.5	3.97	4.47	5.04	5.54
240	1.0	4.54	5.54	5.65	6.65
240	5.0	7.14	12.14	8.55	13.55
	10.0	8.98	18.98	10.61	20.61
	25.0	11.79	36.79	13.73	38.73

# 6.3.2.2. Power Calculations for Evaluation of Immunity

The evaluation of immunogenicity includes the magnitude of the immune response as well as the positive response rate. The primary endpoint is the immune response measured by neutralization assay at 4 weeks after the third product administration. Neutralization assay data are close to being log-normally distribution. Table 7 provides the minimum detectable between-group difference with respect to positive response rate. Table 8 presents the minimum detectable effect size of the between-group difference in log scale with respect to the magnitude of immune response by two-sided t-test. With 1200 subjects per group, the study is capable of detecting the between-group difference with 80% power if the mean of the between-group difference is 0.11 and the standard deviation is 1 on the log scale. If the standard deviation is 0.30, the study is capable of detecting a 0.03 between-group difference with 80% power and 1200 per group.

Table 8:	Minimum Detectable Difference in the Magnitude of Immune Response (log
	transformed) between 2 Groups Assuming Type I Two-Tail Error Rate of 5%

	Subjects within each groun	Minimum detectable effect size		
Standard Deviation	(#)	With 80% power	With 90% power	
	1200	0.11	0.13	
1	960	0.13	0.15	
	480	0.18	0.21	
	240	0.26	0.30	
0.30	1200	0.03	0.04	
	960	0.04	0.04	
	480	0.05	0.06	
	240	0.08	0.09	

# 6.3.2.3. Power Calculations for Evaluation of Efficacy

This trial is designed as an event driven study to test the null hypothesis that VE  $\leq 20\%$ . The efficacy endpoint will be evaluated once a fixed number of ZIKV cases have occurred. Table 9 provides the number of cases that are required to achieve 80% and 90% power for the test of the null hypothesis (VE  $\leq 20\%$ ) for various assumed VEs using the R function binom.power. For this calculation, we note that conditional on the total number of cases, the probability a case comes from the vaccine group is equal to (1-VE)/(2-VE). Thus, the null probability that a case comes from the vaccine is given by (1-0.2)/(2-0.2) = 4/9. Simulations show that power from this conditional binomial calculation is an excellent approximation to the power from a Cox regression model which will be used for analysis. With ninety cases of virologic ZIKV infection, the study is capable of detecting a vaccine efficacy of 61% with 90% power. While these calculations assume there is no interim monitoring and the study will be monitored using an O'Brien-Fleming boundary for efficacy, such monitoring has a negligible impact on power.

# Table 9:Number of Cases of Virologic ZIKV Infection Required to Achieve 80% or 90%
Under Different Vaccine Efficacies by Conditional Binomial Test with Two-
sided Type I Error Rate of 0.05 and Null VE ≤ 20%

Vaccine Efficacy	Cases of ZIKV infection for 80% power (#)	Cases of ZIKV infection for 90% power (#)
0.80	20	27
0.70	37	50
0.61	66	89
0.60	71	95
0.50	150	201

While the study is designed to achieve 90 cases of virologic ZIKV infection, the sample size required to achieve this goal will depend on the duration of the study and the yearly incidence rate in the placebo group. Table 10 provides the expected number of cases of virologic ZIKV infection with 2 or 3 years of follow-up from the start of accrual under different assumptions about the placebo yearly incidence rate while assuming a VE of 61% and a total sample size of 2400. For this calculation, we assume that the 2400 subjects are accrued within 6 months.

Table 10:Expected Number of Cases of Virologic ZIKV Infection within 2 and 3 Years of
Trial Initiation under Different Assumed Yearly Incidence under Placebo with
2400 Subjects

Yearly Incidence of cases of ZIKV infection (under placebo)	Cases of ZIKV infection within 2 years (#)	Cases of ZIKV infection within 3 years (#)
0.005	14	23
0.010	29	45
0.020	57	91
0.030	86	136
0.040	114	181

Therefore, we see that if the placebo incidence rate is 3%, the target of 90 infections will take about 2 years to achieve. If the placebo incidence rate is 2%, the target of 90 infections will take about 3 years to achieve.

The annual incidence of virologic ZIKV cases is uncertain and may be lower than 2%. In addition, at ZIKV endemic sites, some enrollees in the study may have been pre-exposed to ZIKV and are therefore unlikely to become virologic ZIKV cases. To compensate for low incidence and/or baseline seropositive subjects, we may need to expand the sample size. Table 11 gives the expected number of virologic ZIKV cases by 2 or 3 years from a potentially expanded study that accounts for 0% to 30% seropositive enrollees at baseline over a range of annual incidence rates that can be as low as 0.25% under placebo. In these calculations, we assume baseline seropositives will not become infected with ZIKV and the incidence rate applies to the baseline seronegatives and a VE of 61%. We also assume that enrollment is completed within 12 months.

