# 6.4. Statistical Analysis

Study accrual is defined in this protocol as being randomized to a treatment group and receiving the first administration of study product. All accrued subjects will receive at least one product administration and therefore will provide some safety data. The safety population will include all enrolled subjects, summarized according to the actual vaccination dose received.

In **Part B**, all subjects will be tested for baseline ZIKV serostatus based on samples collected at Visit 02 prior to the first product administration. Since those with prior exposure to ZIKV may respond differently to the vaccine from those naïve subjects, safety, immunogenicity and efficacy will be analyzed within each stratum defined by baseline ZIKV status in addition to overall strata combined. **Part A** of the study is to be conducted at endemic or potentially endemic sites with baseline ZIKV serostatus tested, then safety and immunogenicity analyses will be similarly run by stratum in addition to overall strata combined.

Three types of analysis cohorts are defined. The Intent-to-treat (ITT) cohort will include all accrued subjects according to group assignment. The Per Protocol (PP) cohort will include all subjects receiving all planned vaccinations within window as assigned by the randomization schedule, and not experiencing any other major protocol deviations prior to the visit of

evaluation. The Modified intent-to-treat (mITT) analyses will include all accrued subjects who remain event-free one week after all planned product administration, where event is the primary efficacy event of a positive ZIKV PCR test result.

No multiple comparison adjustment will be employed for safety, immunogenicity, or efficacy analyses. Missing data will be primarily considered as missing completely at random in safety and immunogenicity analysis provided missing data is modest (e.g. <5-10%). For completeness, we will examine the missing data completely at random assumption and perform sensitivity analyses which weaken the missing completely at random assumption if the missing data is >10% or if the missing at random assumption is questionable. For efficacy, missing at random will be assumed and methods for handling missingness, such as multiple imputation and inverse propensity weighting, will be considered.

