# 6.4.4. Analysis of ZIKV Incidence

Efficacy evaluation with respect to ZIKV incidence will be performed in **Part B**. Incidence rates for ZIKV cases will be described by vaccine group and by baseline ZIKV stratum for each group. Results will be treated both as dichotomous (infection, no infection) and as a time to event (infection) variables. The primary analysis will be based on the time to case of virologic ZIKV infection, i.e., when a subject is positive for ZIKV based on a PCR test. The time to ZIKV case data, accounting for censoring, will be described using Kaplan-Meier curves and efficacy computed using a Cox proportional hazards model. VE will be estimated by the hazard ratio from the Cox proportional hazards model stratified by baseline ZIKV exposure status.

The primary efficacy analysis is a test of the null hypothesis (H0): the study vaccine has VE no more than 20% in preventing ZIKV infection, i.e., VE  $\leq$  20%, where ZIKV infection is defined as virologically confirmed infection by PCR virus detection. The alternative hypothesis is that VE > 20%. The criterion for success will be that a one-sided test of H0 has p-value  $\leq$  0.025. This primary analysis will be based on the mITT cohort stratified by baseline serostatus (prior exposed to ZIKV or not). If the null VE  $\leq$  20% is not rejected, an additional test of H0\*: VE = 0 will be conducted using a one-sided type I error rate of 0.025.

The secondary efficacy analyses include the testing of this hypothesis over the two stratum combined. Another secondary analysis will test the above hypothesis H0, where ZIKV infection is defined as PCR virus detection irrespective of symptoms. The SAP will provide any necessary additional specificity and/or cohort definitions such as discussed at the beginning of Section 6.4.

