### 6.2. Timing of Analyses

- 1. Interim immunogenicity analyses for **Part A** may be performed on an ongoing basis, per sponsor directive.
  - a) The first interim immunogenicity analysis will be performed when 10 subjects in each group have data available through Visit 05
- 2. Interim immunogenicity analyses for **Part B** may be performed on a subset of subjects after the NAb assays up to and including Week 12 have been completed for the subset of subjects.
- 3. Final Efficacy Analysis will occur when the total number of mITT virologic ZIKV cases (primary efficacy endpoint) in **Part B** of the study reaches 90 or study completion.
- 4. The Final Analysis of safety data for both Part A and Part B will be performed after clinical database lock when all subjects have been followed through 32 weeks after the last product administration for Part A and at least 6 months after the first product administration for Part B. Final analysis of the efficacy and immunogenicity endpoint data will follow the database lock of the immunogenicity and efficacy data once all lab data are received and validated.
- 5. Exploratory Immunogenicity Analyses may be completed following database lock as assay results become available.

For all analyses completed prior to database lock, individual subjects' study group assignments will not be unblinded with the possible exception of a review of selected AEs or episodes of ZIKV disease for safety monitoring requirements, as described in the Study Blinding Plan.

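### Tables 10 and 11 count cases from Day 0 with no dropout, whereas the primary test counts mITT cases from about Day 63, so the tables overstate expected primary cases by roughly 10% at 2 years and 6–7% at 3 years

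*Combined protocol and SAP*

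**What the plan says.** Protocol 6.3.2 sets the target: "the trial aims to achieve 90 cases of naturally acquired virologic ZIKV infection within 2 to 3 years". Protocol 6.3.2.3 links that count to power: "With ninety cases of virologic ZIKV infection, the study is capable of detecting a vaccine efficacy of 61% with 90% power". Table 10 gives expected cases for 2,400 subjects accrued within 6 months at VE 61%. Its 3% row shows 86 at 2 years and 136 at 3 years, and the text concludes that "if the placebo incidence rate is 3%, the target of 90 infections will take about 2 years to achieve". Table 11 assumes 12-month enrolment and baseline seropositive rates of 0% to 30%. The text after it, like Protocol 6.3.2, concludes that 15,000 subjects reach the target within 3 years at 0.5% incidence with 30% seropositive. Neither table states a dropout rate or a delay before cases count.

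The primary test (Protocol 6.4.4, SAP 10.2) is run in the mITT cohort. "The criterion for success will be that a one-sided test of H0 has p-value" of at most 0.025. Protocol 6.4 defines mITT as "all accrued subjects who remain event-free one week after all planned product administration", and SAP 6.3 carries the same rule. The third administration is at Week 8. SAP 6.2, item 3, names mITT cases in its trigger for the final efficacy analysis (90 cases or study completion): "when the total number of mITT virologic ZIKV cases (primary efficacy endpoint". SAP 2.1 and SAP 10 agree. Protocol 6.4.5 ties the interim looks at 30 and 60 cases to mITT, but describes the final 90 only as virologic cases in Part B.

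On re-estimation before randomization ends, Protocol 6.3.2 says: "This calculation will explicitly take into account the accrual rate, the dropout rate, the baseline seropositive rate, and the incidence rate".

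**The concern.** The quantity tabulated is not the quantity tested. A subject who becomes a case before about Day 63 leaves the mITT cohort, so the first nine weeks of each subject's follow-up can add nothing to the 90 primary cases. SAP 10.2 starts the time-to-event clock at the first administration, but this does not bring those early cases back.

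Tables 10 and 11 support the choice of 2,400 subjects and the ceiling of 15,000. They also show what a calculation for the keep-or-expand decision might look like. If that calculation follows their method, it will overstate how soon the primary test has 90 events. The re-estimation inputs listed in Protocol 6.3.2 include dropout but not the mITT start.

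**Working it through.** **Inputs.**
- N = 2400, 1:1 allocation, VE 61% (hazard ratio 0.39), 6-month accrual: Table 10.
- 12-month enrolment: Table 11.
- mITT start at Week 8 plus one week: 63 days = 63/365.25 = 0.1725 year.
- Follow-up of 96 weeks per subject: 672/365.25 = 1.84 years (Précis).
- Uniform accrual is my assumption, so mean entry is 0.25 year in Table 10 and 0.5 year in Table 11.

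**Formula (linear form).** Expected cases = (N/2) × (1 − seropositive rate) × incidence × (1 + 0.39) × mean person-years per subject. The exponential form replaces incidence × time with 1 − exp(−rate × time), averaged over entry times. Ranges below run from exponential to linear.

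**Reproducing the plan.**
- Table 10, 3%: 1200 × 0.03 × 1.39 = 50.04 cases per year of mean exposure. At 2 years, 50.04 × 1.75 = 87.6 (exponential 85.7), stated 86. At 3 years, 50.04 × 2.75 = 137.6 (exponential 133.0), stated 136.
- Table 11, 7,500 at 1%, none seropositive: 3750 × 0.01 × 1.39 = 52.1; × 1.5 = 78.2, stated 78.
- Table 11, 15,000 at 0.5%, 30% seropositive: 7500 × 0.7 × 0.005 × 1.39 = 36.49; × 2.5 = 91.2, stated 91.
- Taken together, the rounded Table 10 cells imply mean exposure of 1.709–1.716 years at 2 years. Day 0 counting gives 1.75. A Day 63 start gives 1.75 − 0.1725 = 1.5775, which does not reproduce the table.

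So the tables count from Day 0 with nobody lost. (Two Table 11 rows are printed with incidence 0.0250, but their counts fit 0.0025.)

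**Counting from Day 63, no dropout.**

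| Scenario | Stated | mITT cases |
|---|---|---|
| Table 10, 3%, 2 years | 86 | 50.04 × 1.5775 = 78.9 (exponential 77.1) |
| Table 10, 2%, 3 years | 91 | 33.36 × 2.5775 = 86.0 (exponential 83.9) |
| Table 11, 7,500 at 1%, 2 years | 78 | 52.1 × 1.3275 = 69.2 (exponential 68.7) |
| Table 11, 15,000 at 0.5%, 30% seropositive, 3 years | 91 | 36.49 × 2.3275 = 84.9 (exponential 84.5) |

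**Proportional loss.** At 2 years, 0.1725/1.75 = 9.9% (Table 10) and 0.1725/1.5 = 11.5% (Table 11). At 3 years, 0.1725/2.75 = 6.3% and 0.1725/2.5 = 6.9%.

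**Time to 90 mITT cases at 3%.** 90/50.04 + 0.25 + 0.1725 = 2.22 years (exponential 2.27), against 2.05 (2.09) when counting from Day 0.

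**Dropout.** The documents give no rate for efficacy. Assuming 5%, 10% or 20% lost at a constant rate over 96 weeks, the 3%/2-year cell becomes about 75, 73 or 69 mITT cases.

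**Power at VE 61%.** A normal approximation with null probability 4/9 and alternative 0.39/1.39 gives 90% at 90 cases, about 85% at 77 and about 81% at 69.

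**If the trigger is all virologic cases.** At 3% incidence, about 50.04 × 0.1725 = 8.6 of the 90 fall before Day 63. The primary test would then have about 81 events and about 87% power.

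**The case against.** The strongest reply is that nothing is miscalculated. Both tables follow from their stated assumptions, apart from the two misprinted incidences, and their titles say virologic infection, which is what they count. Under the Protocol 6.4.5 wording (90 virologic cases in Part B), Table 10 counts the trigger event, and 3% gives 90 at 2.05–2.09 years before dropout. The sentence says about 2 years and is drawn from a cell showing 86, so it is openly approximate. A shift to 2.2–2.3 years stays inside the planned 2 to 3 years and is small beside an incidence range of 0.5% to 4%. The trial is event-driven, so the 90% power belongs to 90 cases and not to Table 10. The re-estimation already lists dropout, enlargement to 15,000 is allowed, and the expected time to 90 cases is reviewed periodically.

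Most of this stands, and it limits the point. Two things remain. The primary test uses mITT cases whichever trigger applies; under the Protocol 6.4.5 wording the shortfall appears as fewer than 90 events in that test. The mITT start is also absent from the listed re-estimation inputs.

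A reader might also infer that the plan assumes 20% dropout for efficacy. It does not. The phrase "960 samples per group to account for 20% early drop out" is one safety scenario for Table 7, beside 1200, 480 and 240 per group, and Protocol 6.3.2 says the dropout rate will come from trial data and other sources.

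**Conclusion.** The tables overstate expected primary cases in every cell: by about 10% (Table 10) to 11–12% (Table 11) at 2 years, and by 6–7% at 3 years. This comes from an unstated assumption that does not match the primary cohort; it is not a calculation error. At 3% and N = 2400 the 2-year figure is about 77–79 mITT cases, 11 to 13 short of 90. The statement most clearly not met is the one for 15,000 subjects at 0.5% with 30% seropositive, where about 85 are expected at 3 years. These figures assume uniform accrual, no dropout, and all subjects on schedule for the third administration. Dropout lowers them further, by an amount the documents do not let one fix.

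A reader might go on to infer that 90 cases cannot be reached at 3%, or that the 2-year sentence is plainly false. The Day 63 start alone does not show this. The first inference also needs the 96-week limit on each subject's follow-up, which is a separate issue. With that limit and no dropout, at most about 81–83 mITT cases are expected (linear: 50.04 × (1.84 − 0.1725) = 83.4). Without it, 90 are reached about nine weeks later than with Day 0 counting.

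**What to change.** 1. Recompute Tables 10 and 11 with person-time starting at Day 63, and show a stated range of dropout rates labelled as assumptions. Correct the two 0.0250 entries at the same time.
2. Restate the 3%/2-year sentence, and the 15,000/3-year sentence both in Protocol 6.3.2 and after Table 11.
3. Add the mITT start to the re-estimation inputs listed in Protocol 6.3.2.
4. Reconcile Protocol 6.4.5 (90 virologic cases in Part B) with SAP 2.1, 6.2 and 10 (90 mITT cases), so that one definition governs the final analysis.

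The cost is recalculation and wording, with somewhat less favourable expected counts. These edits need no change to the design or to the stated power at 90 cases.

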	The vaccine dose and administration plan for Part B was selected based on Part A and Phase 1 data. Vaccine efficacy will be evaluated in Part B by comparing incidence of ZIKV cases between vaccine and placebo groups. During the study, when subjects exhibit any possible symptom of ZIKV infection, they will be evaluated by blood and urine ZIKV polymerase chain reaction (PCR). Stored blood and urine samples will also be assessed retrospectively by ZIKV PCR to identify possible asymptomatic cases. A Data and Safety Monitoring Board (DSMB) will oversee the study.

Part A									
Crown		Tetal Deres	Number of Injections per Dose	Number of Limbs: Location of Injections	Administration Schema				
Group	Subjects	Total Dose			Day 0	Week 4	Week 8		
1	30	4 mg	2 2 limbs: both arms			DNA	DNA		
2	30	4 mg	4	4 limbs: both arms and legs	DNA	DNA	DNA		
3	30	8 mg 4 4 limbs: DNA DNA D							
Total	Total         90*         Study product is administered IM by needle-free injection device.								
*Accrual up	to a total of	100 subjects is	s permitted if add	itional subjects are no	eeded for sa	afety evaluat	tions.		
			Par	t B					
C		T ( 1 D	Number of	Number of Limbs:	Admir	nistration S	chema		
Group	Subjects	Total Dose	Injections per Dose	Location of Injections †	Day 0	Week 4	Week 8		
4	1200	4 mg	2	2 arms	DNA	DNA	DNA		
5	1200	0	2	2 arms	Placebo	Placebo	Placebo		
Total         2400         Study product is administered IM by needle-free injection device.									
† Preferred location of injections is in both arms. Administration in the thighs may be allowed with IND Sponsor approval.									

The product administratio	n schema is as follows:
---------------------------	-------------------------

Duration:Part A: Each subject will be followed for 32 weeks.Part B: Each subject will be followed for 96 weeks.

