## 4.1.1. Inclusion Criteria

A subject must meet all of the following criteria:

1. Part A: 18 to 35 years of age;

Part B: 15 to 35 years of age

2. Part A: Available for clinical follow-up through Study Week 32;

Part B: Available for clinical follow-up through Study Week 96

- 3. Able to provide proof of identity to the satisfaction of the clinician completing the enrollment process
- 4. Able and willing to complete the informed consent/assent process
- 5. Able and willing to complete the Assessment of Understanding and to verbalize understanding of all questions answered incorrectly prior to signing consent/assent
- 6. Willing to donate blood and urine to be stored and used for future research
- 7. In good general health without clinically significant medical history
- 8. Physical examination and laboratory results without clinically significant findings within the 56 days prior to randomization
- 9. Weight > 30 kg
- 10. Agree not to receive any licensed or investigational flavivirus vaccines through 4 weeks after the last product administration
- 11. **Part A**: Accessible injection sites on each limb as follows: 1 injection site in the deltoid muscle of each arm and 1 injection site in the vastus lateralis muscle of each anterolateral thigh.

**Part B**: Accessible injection sites on the deltoid muscle of each arm. Injection sites on the vastus lateralis muscle of the anterolateral thighs may be allowed with IND Sponsor approval if an injection site on each deltoid muscle is not available.

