# Table 11:Expected Number of Cases of Virologic ZIKV Infection among Seronegative
Enrollees within 2 and 3 Years of Trial Initiation under Different Assumed
Baseline Seropositive Rates, Yearly Incidence Rates under Placebo among
Seronegatives, and Sample Sizes

Seropositive rate at baseline (%)	Total sample size (#)	Yearly incidence (under placebo)	Cases of ZIKV infections within 2 years (#)	Cases of ZIKV infections within 3 years (#)
0	7500	0.0100	78	130
	12500	0.0050	65	108
	15000	0.0050	78	130
	15000	0.0025	39	65
10	7500	0.0100	70	117
	12500	0.0050	58	97
	15000	0.0050	70	117
	15000	0.0025	35	58
	20000	0.0025	47	78
30	7500	0.0100	54	91
	12500	0.0050	45	76
	15000	0.0050	54	91
	15000	0.0250	27	45
	25000	0.0250	45	76

If the seropositive rate at baseline is no more than 30% and the yearly incidence for cases of virologic ZIKV infection is 0.005, i.e., 0.5% under placebo, then with VE of 61%, an expanded study of size 15000 reaches the targeted 90 cases of ZIKV infections within 3 years if enrollment is completed within 12 months.

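### The 3-year case projections in Tables 10 and 11 count follow-up beyond Week 96; under the protocol's own follow-up the two headline scenarios yield about 61 and 67 cases, not 91

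*Combined protocol and SAP*

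**What the plan says.** The sample size text for Part B (protocol 6.3.2 and 6.3.2.3) projects when 90 virologic cases will be reached. Table 10 gives the "expected number of cases of virologic ZIKV infection with 2 or 3 years of follow-up from the start of accrual" for 2400 subjects accrued in 6 months. Table 11 does the same for larger samples accrued in 12 months, with 0% to 30% of enrollees seropositive and not at risk. Both assume a vaccine efficacy of 61%.

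Three conclusions are drawn from the 3-year columns:

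- Section 6.3.2.3, after Table 10: "If the placebo incidence rate is 2%, the target of 90 infections will take about 3 years to achieve".
- Section 6.3.2, on the ceiling of 15,000: "Such a sample size could achieve our target number of virologic ZIKV cases within 3 years, assuming full accrual within 12 months", even at 0.50% incidence with 30% seropositive.
- Section 6.3.2.3, after Table 11: "an expanded study of size 15000 reaches the targeted 90 cases of ZIKV infections within 3 years if enrollment is completed within 12 months", for the same incidence and seropositivity.

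Individual follow-up is fixed elsewhere. The Précis says: "Part B: Each subject will be followed for 96 weeks". Inclusion criterion 2 in section 4.1.1 reads: "Part B: Available for clinical follow-up through Study Week 96". Sections 4 and 4.2.6 repeat the 96 weeks. The last visit in Appendix III Table C is Visit 26 at Week 96 (Day 672). SAP section 10.2 censors uninfected subjects at study completion or early termination.

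**The concern.** The tables run on calendar time and let each subject contribute person-time until year 3. The protocol stops observing each subject at Week 96. With 6-month accrual the last subject leaves at 0.5 + 1.84 = 2.34 years; with 12-month accrual, at 1 + 1.84 = 2.84 years. No case can be observed after that, so the interval up to year 3 adds nothing.

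These sentences tell the reader which incidence and seroprevalence 2400 subjects, and the 15,000 ceiling, can absorb. If they are too favourable, the case for the ceiling fails in the scenario used to support it. SAP section 2.1 places the final analysis at 90 mITT cases or at study completion, so the trial could finish well short of 90 cases with power below plan.

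**Working it through.** **Inputs.** 1:1 allocation (6.3.2). VE 61%, so the vaccine arm has 0.39 of the placebo incidence. Accrual 0.5 year (Table 10) or 1 year (Table 11), taken as uniform, which is my assumption. Seropositives contribute no cases. No dropout. Cap = 96 × 7 / 365.25 = 1.84 years.

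**Formula.** Expected cases = (N/2) × (1 − seropositive share) × placebo incidence × 1.39 × mean follow-up.

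**Step 1: reproduce the printed figures.** Without a cap, mean follow-up at year 3 is 3 − accrual/2, which is 2.75 years (Table 10) and 2.5 years (Table 11).

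- 2400 at 2%: 1200 × 0.02 × 1.39 × 2.75 = 91.7 (printed 91).
- 15,000 at 0.5%, 30% seropositive: 7500 × 0.70 × 0.005 × 1.39 × 2.5 = 91.2 (printed 91).

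Exponential event times give 89.7 and 90.7. The remaining rows reproduce closely, except the last two of Table 11. Those print incidence 0.0250, but their counts fit 0.0025. At 0.025, 15,000 subjects would give about 444 cases by year 3 (exponential), not 45. The text before the table speaks of "annual incidence rates that can be as low as 0.25% under placebo", so this is a misprint.

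**Step 2: cap follow-up at 96 weeks.** By year 3 every subject has completed 1.84 years.

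- 2400 at 2%: 1200 × 0.02 × 1.39 × 1.84 = 61.4 (exponential 60.5).
- 15,000 at 0.5%, 30% seropositive: 7500 × 0.70 × 0.005 × 1.39 × 1.84 = 67.1 (exponential 66.9).

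Full 3-year columns in printed order:

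| Block | Printed | Capped, linear | Capped, exponential |
|---|---|---|---|
| Table 10 | 23, 45, 91, 136, 181 | 15.3, 30.7, 61.4, 92.1, 122.8 | 15.3, 30.5, 60.5, 90.0, 119.1 |
| Table 11, 0% | 130, 108, 130, 65 | 95.9, 79.9, 95.9, 48.0 | 95.2, 79.6, 95.5, 47.9 |
| Table 11, 10% | 117, 97, 117, 58, 78 | 86.3, 71.9, 86.3, 43.2, 57.5 | 85.7, 71.7, 86.0, 43.1, 57.4 |
| Table 11, 30% (last two at 0.0025) | 91, 76, 91, 45, 76 | 67.1, 55.9, 67.1, 33.6, 55.9 | 66.6, 55.7, 66.9, 33.5, 55.8 |

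Eleven 3-year entries are printed at 90 or more. Seven of them fall clearly below 90.

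**Step 3: power at the reduced counts.** This uses the protocol's conditional binomial test, p0 = 4/9 and p1 = 0.39/1.39, one-sided 0.025.

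| Cases | Exact | Normal approximation |
|---|---|---|
| 60 | 0.69 | 0.745 |
| 61 | 0.755 | 0.75 |
| 67 | 0.77 | 0.79 |
| 90 | 0.89 | 0.90 |

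Table 9 asks for 66 cases for 80% power. The first scenario falls below that; the second just meets it.

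**Step 4: what would give 90 cases under the cap.** At N = 2400, placebo incidence of 2.9% (linear) to 3.0% (exponential). At N = 15,000 with 30% seropositive, 0.67%. At 0.5%, 15,000 suffices only with seropositivity up to about 6%: 1 − 90/95.5 = 5.8% exponential, 1 − 90/95.9 = 6.2% linear. Alternatively, about 3,520 to 3,570 subjects at 2%, or 20,100 to 20,200 at 0.5% with 30% seropositive.

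**Step 5: sensitivity.** These figures are exponential unless marked.

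- Latest in-window visits (Visit 04 +14 days, Visit 26 +7 days, so 99 weeks): 62.3 and 69.0.
- A 104-week cap (linear): 66.5 and 72.7.
- Only mITT cases counted, after Week 9: 54.7 and 60.6.
- mITT cases with an assumed 20% dropout over 96 weeks: 48.5 and 53.7. The 20% appears in the protocol only in the safety power text (6.3.2.1).

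**The case against.** The strongest reply is that the tables are correct for the assumption they declare, and that the operative decision does not rest on them. Section 6.3.2.3 concedes that incidence may be below 2%. Section 6.3.2 re-estimates the sample size before randomization ends: "This calculation will explicitly take into account the accrual rate, the dropout rate, the baseline seropositive rate, and the incidence rate". Section 6.4.5 and SAP 6.6.3 add blinded incidence monitoring and allow stopping for lack of feasibility. On this view the projections are illustrative, and the primary test, boundaries and Table 9 are untouched.

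Much of that is true. The multiplication is sound; the fault is an assumption that conflicts with the stated follow-up. But the re-estimation does not correct the three sentences or the justification of the 15,000 ceiling. Its listed inputs do not name the 96-week limit. They may cover only rates to be estimated, so the omission does not show that the limit will be ignored, but naming it would remove the doubt.

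Three points on size also stand. Exact binomial power moves in steps, so 69% at 60 cases overstates the loss; about 75% is fairer. The 15,000 scenario still has roughly 80% power by Table 9. The event model matters in the upper rows of Table 10: at 3% the capped count is 92.1 linear or 90.0 exponential, so that row reaches the target with little or no margin (at about 2.3 years in the exponential model). None of this brings either headline scenario near 90.

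**Conclusion.** The concern holds. The three sentences claim a case yield that the 96-week follow-up cannot deliver. At 2% with 2400 subjects the expected count is about 61 rather than 91. At 0.5% with 30% seropositive and 15,000 subjects it is about 67 rather than 91. Power at VE 61% is about 75% and 79% against a planned 90%. The result assumes uniform accrual, no dropout and no observation after Week 96. Dropout or counting mITT cases alone lowers the counts further, and no variant examined restores 90.

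Not affected: the 2-year columns (57.5 becomes 56.7 at 2%, exponential), 2400 subjects at 3% in total yield, 15,000 at 0.5% with seropositivity up to about 6%, Table 9, power once 90 cases exist, and type I error. The statements are wrong as written and should be corrected.

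**What to change.** 1. Recompute the 3-year columns of Tables 10 and 11 with person-time capped at 96 weeks, and state the event model used. The capped values are tabulated above; the choice of model matters mainly for the 3% and 4% rows of Table 10.
2. Reword the three sentences in 6.3.2 and 6.3.2.3. Give either the incidence and seroprevalence at which 2400 and 15,000 deliver 90 cases (about 3% for 2400; about 0.67% for 15,000 with 30% seropositive), or the power those samples deliver at 2% and at 0.5% with 30% seropositive.
3. If follow-up past Week 96 was intended, state it and reconcile the Précis, sections 4, 4.1.1 and 4.2.6, and Appendix III.
4. Name the 96-week limit among the inputs to the re-evaluation in 6.3.2.
5. Show mITT-only counts and any assumed dropout as labelled sensitivity rows.
6. Correct 0.0250 to 0.0025 in the last two rows of Table 11.

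The cost is one planning calculation and some protocol wording. Unless item 3 applies, it adds no subjects, visits or assays. The stated figures become less favourable.
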